## **5. STUDY MANAGEMENT**

### **5.1 Monitoring**

#### **5.1.1 Study monitoring**

The monitoring of this study will be performed in accordance with the principles of Good Clinical Practice (GCP) as laid out in the International Conference on Harmonisation (ICH) document “Good Clinical Practice: Consolidated Guideline”.

#### **5.1.2 Data verification**

It is a prerequisite of this study that the study monitor has direct access to source data for data verification. This will be done by comparing data from the CRFs with those in the subject’s medical notes (permission from the subject will be sought as part of the consent process). Such verification is an essential element of quality control, as it allows the rectification of transcription errors and omissions.

For this study original data regarded as source data are defined by a source data verification plan.

Monitoring including source data verification should routinely be performed prior to the transfer of data to Data Management.

#### **5.1.3 Archiving of study documents**

The Investigator Study File (ISF) must be archived for at least 10 years after the study report is finalized.

### **5.2 Audits and inspections**

Authorised representatives of AstraZeneca, a regulatory authority or an Ethics Committee may visit the centre to perform audits or inspections, including source data verification. The purpose of an AstraZeneca audit or inspection is to systematically and independently examine all study-related activities and documents to determine whether these activities were conducted, and data were recorded, analysed, and accurately reported according to the protocol, GCP guidelines of the ICH and any applicable regulatory requirements. The investigator should contact AstraZeneca immediately if contacted by a regulatory agency about an inspection at his or her centre.

### **5.3 Training of staff**

The principal investigator will maintain a record of all individuals involved in the study (medical, nursing and other staff). He or she will ensure that appropriate training relevant to the study is given to all of these staff, and that any new information of relevance to the performance of this study is forwarded to the staff involved.

## **5.4 Changes to the protocol**

Study procedures will not be changed without the mutual agreement of the principal investigator and AstraZeneca.

If it is necessary for the study protocol to be amended, the amendment and/or a new version of the study protocol must be notified to or approved by each Ethics Committee, and in many countries also the local regulatory authority, before implementation. Local requirements must be followed.

AstraZeneca will distribute amendments and new versions of the protocol to each principal investigator(s) who in turn is responsible for the distribution of these documents to his or her Ethics Committee, and to the staff at his or her centre. The distribution of these documents to the regulatory authority will be handled according to local practice.

## **5.5 Study agreements**

The principal investigator at each centre must comply with all the terms, conditions, and obligations of the study agreement for this study. In the event of any inconsistency between this protocol and the study agreement, this protocol shall prevail.

## **5.6 Study timetable and end of study**

The study is expected to start in May 2007 and to be completed by September 2007. End of study is defined as database lock (estimated to September 2007), which is the time point after which no subject will be exposed to study-related activities

## **5.7 Data management**

### **5.7.1 Case report forms**

Paper CRFs (pCRFs) will be used to record all data not captured electronically. Data should be recorded legibly onto the pCRFs in blue or black ballpoint pen. Correction fluid or covering labels must not be used.

The AstraZeneca Monitor will check data at the monitoring visits to the study site. The Investigator will ensure that the data in the pCRFs are accurate, complete and legible.

Data from the completed pCRFs will be entered onto AstraZeneca's clinical study database and validated as described in the data management plan. Any missing, impossible or inconsistent recordings in the pCRFs will be referred back to the Investigator using a data query form and be documented for each individual subject before clean file status is declared.

The data management plan (DMP) will describe the methods used to collect, check and process clinical data in detail. It will also clarify the roles and responsibilities for the different functions and personnel involved in the data management process. Further, the DMP will also describe the data flow and timelines within the study. For more information, see the DMP.

## **6. PHARMACOKINETIC, PHARMACODYNAMIC, SAFETY, GENETIC AND STATISTICAL METHODOLOGY**

### **6.1 Pharmacokinetic / pharmacodynamic evaluation**

#### **6.1.1 Calculation or derivation of pharmacokinetic variables**

The PET- pharmacokinetic analyses will be performed at AZ, by joint work of PET-pharmacokineticist and pharmacokineticists from Dept. of Clinical Pharmacology, AstraZeneca.

#### **6.1.2 Regions of interest (ROIs) in the PET measurement**

Before delineation of region of interests (ROIs) the orientation of the brain is spatially normalised by having the high resolution T1-images reoriented according to the line defined by the anterior and posterior commissures (ac-pc line) being parallel to the horizontal plane and the inter-hemispheric plane parallel to the sagittal plane. The PET images are co-registered to the high-resolution T1-weighted MRI into the same space using Statistical Parametric Mapping 2 (SPM2) (Wellcome Department of Cognitive Neurology, UK). The delineations of anatomical brain regions are made manually on the co-registered MRI images using in-house image analysis software, Human Brain Atlas (Hba). The main target ROI for NET measurements will be thalamus. If possible (due to relatively low signal-noise ratio), ROI of the midbrain, or even more precisely - locus coeruleus- will be investigated. The reference region for NET binding will be caudate nucleus, presumed to have low NET density (less than 10%). In addition, other regions may be outlined based on the observed distribution of radioactivity in the brain. The ROIs will be displayed on the corresponding PET images and pooled for each anatomical region.

#### **6.1.3 Pharmacokinetic evaluation of PET data**

The radioactivity concentration in each ROI is calculated for each sequential frame, corrected for F decay, and plotted versus time (CROI). The results will be presented as time-activity (TACT) data for brain tissue, given as radioactive concentration (nCi/mL).

##### **6.1.3.1 Occupancy and the relationship to plasma exposure**

An index of NET density, binding potential (BP) will be calculated using ratio method (Farde et al 1989), a graphical linear analysis (Logan et al 1990). The most appropriate method(s) for the calculation of BP will be then used for further calculation of occupancy.

The occupancy will be calculated according to the equation:

$$\text{Occupancy}(\%) = \frac{BP_{\text{Baseline}} - BP_{\text{drug}}}{BP_{\text{baseline}}} \cdot 100$$

The relationship between exposure and NET occupancy will be evaluated using PK/PD modelling procedures, based on the equations:

$$Occupancy(\%) = \frac{Occ_{max} \cdot Dose}{ED_{50} + Dose}$$

$$Occupancy(\%) = \frac{Occ_{max} \cdot C_{av,PET}}{EC_{50} + C_{av,PET}}$$

where  $ED_{50}$  represents the SQL SR dose corresponding to a 50% occupancy and  $EC_{50}$  represents the plasma concentration of quetiapine or its major active metabolite NDAQ corresponding to 50% occupancy.  $Occ_{max}$  is the maximum achievable occupancy and  $C_{av,PET}$  is the average plasma concentration during the PET experiment.

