## LIST OF ABBREVIATIONS AND DEFINITION OF TERMS

The following abbreviations and special terms are used in this study protocol.

Abbreviation or special term	Explanation
AE	Adverse event
AUC PET	Area under plasma concentration-time curve corresponding to the PET-assessment planned at 5 to 7 hr post-dose
BMI	Body mass index
BP	Binding potential
C av,PET	Average plasma concentration during the PET-assessment planned at 5 to 7 hr post-dose.
C max	Maximum (peak) plasma drug concentration
CRF	Case report form
CPU	Clinical Pharmacology Unit
DMP	Data Management Plan
EC 50	Plasma drug concentration corresponding to 50% occupancy of NET
ECG	Electrocardiogram
ED	Effective dose, parameter evaluation risk from radiation exposure
ED 50	Dose of drug inducing 50% occupancy of NET
Ethics Committee	Synonymous to Institutional Review Board and Independent Ethics Committee
Euratom	European Atomic Energy Community
FDA/RDRC	Federal Drug Agency: Radioactive Drug Research Committee
GAD	Generalised Anxiety Disorder
GCP	Good Clinical Practice
HBA	Human Brain Atlas
HBV	Hepatitis B virus
HCV	Hepatitis C virus
HIV	Human Immunodeficiency virus
ICH	International Conference on Harmonisation
IR	Immediate release
IRB	Institutional Review Board
[REDACTED]	[REDACTED]

Abbreviation or special term	Explanation
[REDACTED]	[REDACTED]
LSD	Lysergic acid diethylamide
MDD	Major Depressive Disorder
MRI	Magnetic Resonance Imaging
NET	Noradrenaline (norepinephrine) transporter
NDAQ	N-desalkyl-quetiapine (AZ10081909)
OAE	Other Significant Adverse Event (ie, adverse events of particular clinical importance, other than SAEs and those AEs leading to discontinuation of the subject from study treatment; see definition in Section 4.7.1.1).
PD	Pharmacodynamics
PET	Positron Emission Tomography
PK	Pharmacokinetics
Principal investigator	A person responsible for the conduct of a clinical study at a study site. Every study centre has a principal investigator.
ROI	Region of Interest
SAE	Serious adverse event
SQL	Seroquel
SR	Sustained release
(S,S)[  F]FMeNER-D 2	(S, S)-2-( $\alpha$ -(2-methoxyphenoxy)benzyl)morpholine
SUV	Standard uptake values
TAC	Time-activity curve
T max	Time to reach maximum drug plasma concentration
T 1/2	The terminal elimination half-life
VAS	Visual Analogue Scale
WHO	World Health Organisation

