### **6.3.3 Methods of statistical analyses**

The statistical analysis will be descriptive and exploratory. The safety, tolerability, and pharmacokinetic variables will be analysed using subject listings and, if applicable, summary statistics comprising mean, median, standard deviation, min, and max in the case of continuous variables and frequency distributions in the case of categorical variables. Graphical analysis may also be used for further description of the results.

Exploratory analyses of the relationships between dose, plasma concentration of quetiapine and NDAQ, and NET occupancy will be made by fitting nonlinear models reflecting the theoretical relationships described in Section 6.1.3.1.

Details will be given in the SAP.

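### ED50 and EC50 are defined as giving 50% NET occupancy, but the printed equations make them the values giving half of Occ_max; the two agree only if Occ_max is 100%, which the protocol does not state

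*Protocol*

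**What the plan says.** Protocol Section 6.1.3.1 gives two models, written here in plain notation:

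- Occupancy (%) = Occ_max × Dose / (ED50 + Dose)
- Occupancy (%) = Occ_max × C_av,PET / (EC50 + C_av,PET)

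The sentence below them says that ED50 "represents the SQL SR dose corresponding to a 50% occupancy and" that EC50 "represents the plasma concentration of quetiapine or its major active metabolite NDAQ corresponding to 50% occupancy". Occ_max, it says, "is the maximum achievable occupancy and" no value is given for it. The abbreviation list repeats the two definitions: ED50 is "Dose of drug inducing 50% occupancy of NET" and EC50 is "Plasma drug concentration corresponding to 50% occupancy of NET".

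Section 6.3.3 ties the analysis to these equations. The exploratory analyses "will be made by fitting nonlinear models reflecting the theoretical relationships described in Section 6.1.3.1", with details left to the SAP. Section 2.1 makes the dose–occupancy and concentration–occupancy relationships a primary objective, without naming ED50 or EC50.

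**The concern.** The equations and the definitions cannot both be right unless Occ_max is exactly 100%. The equations carry Occ_max as a separate quantity, described as a maximum that can be achieved, and that symbol would be unnecessary if 100% were meant. The absolute definition appears in two places, so it is not a single slip of wording.

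At stake is how the results are read. These are the only models named for the relationships in the primary objective, and ED50 and EC50 are their location parameters. If Occ_max is estimated and the report uses the printed definition, it will name a dose or concentration as giving 50% occupancy when the fitted curve says otherwise.

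**Working it through.** **Inputs.** The two equations and the definitions come from Section 6.1.3.1 and the abbreviation list. The protocol gives no value for Occ_max, so every Occ_max below is an assumption, chosen to show a range.

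**Step 1: occupancy at ED50.** Put Dose = ED50 in the first equation:

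Occ_max × ED50 / (ED50 + ED50) = Occ_max / 2.

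The same substitution with C_av,PET = EC50 also gives Occ_max / 2. The protocol's 50% is reproduced only when Occ_max = 100%.

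**Step 2: the dose that does give 50% occupancy.** Set the equation equal to 50 and solve for the dose D:

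Occ_max × D = 50 × (ED50 + D)

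D × (Occ_max − 50) = 50 × ED50

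D = ED50 × 50 / (Occ_max − 50).

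This has a positive solution only if Occ_max exceeds 50%. The formula for concentration is the same with EC50.

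**Step 3: numbers.**

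| Assumed Occ_max (%) | Occupancy at ED50 or EC50 (%) | Value for 50% occupancy, as a multiple of ED50 or EC50 |
|---|---|---|
| 120 | 60 | 50/70 = 0.71 |
| 100 | 50 | 50/50 = 1.00 |
| 95 | 47.5 | 50/45 = 1.11 |
| 90 | 45 | 50/40 = 1.25 |
| 80 | 40 | 50/30 = 1.67 |
| 70 | 35 | 50/20 = 2.5 |
| 60 | 30 | 50/10 = 5 |
| 50 | 25 | does not exist |

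**Step 4: an illustration.** The occupancies here are assumed; both doses lie within those Section 3.4.2 allows. Suppose 300 mg gives 60% and 100 mg gives 40%. The printed equation then fits exactly with Occ_max = 80% and ED50 = 100 mg:

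- 80 × 300 / (100 + 300) = 60
- 80 × 100 / (100 + 100) = 40

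Under the printed definition, 100 mg would be reported as the dose giving 50% occupancy, although occupancy at 100 mg is 40%. The same curve reaches 50% at 100 × 50/30, about 167 mg.

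**The case against.** The strongest reply is that this is a matter of labels. Four parts of it stand.

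- The protocol does not say whether Occ_max is estimated or fixed, and Section 6.3.3 leaves the fitting details to an SAP that is not at hand. If Occ_max is fixed at 100%, the definitions are correct. Estimation is the natural reading of the text, but it is an inference.
- If Occ_max is estimated, the fitted curve, Occ_max, ED50 and EC50 are numerically unaffected. Anyone given both parameters can recover the 50% point from the equation.
- ED50 and EC50 are not named as primary endpoints, and Section 6.3.3 calls the analysis descriptive and exploratory.
- No decision rule uses them. Section 6.4 bases the Panel B and C doses on the observed relationships, and after Panel A there is only one dose level, so ED50 and Occ_max could not both be estimated from dose at that point.

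A reader might infer that the study's primary potency figures will be misreported, and always in the direction that makes the drug look more potent. The documents do not support that. Misreporting depends on Occ_max being estimated and differing from 100%. The direction depends on the fit as well: with six to nine subjects and no stated constraint, an estimate above 100% is possible, and the label would then understate potency (0.71 times at 120%).

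The reply does not remove the contradiction. The protocol itself prints both the equation and the definition, so an SAP could resolve the conflict only by adding to this text or departing from it.

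**Conclusion.** The definitions of ED50 and EC50 are wrong as written for the equations they accompany, unless Occ_max is 100%. This follows from algebra on the protocol's own text.

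The size depends on an Occ_max the protocol does not give. At 100% there is no discrepancy, and at 95% the 50%-occupancy value is only 11% above the reported parameter. It is 25% above at 90%, 67% above at 80% and five times the parameter at 60%. At 50% or below, a fit would still return an ED50 although 50% occupancy is never reached.

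This is a minor to moderate point. It affects what the reported parameters mean, in exploratory modelling that serves a primary objective. It does not affect the data, the fitted curve, the conduct of the study or any decision rule in the protocol.

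**What to change.** In Section 6.1.3.1 and the abbreviation list, define ED50 and EC50 as the dose or plasma concentration giving 50% of Occ_max, and report each with the Occ_max estimate from the same fit. If an absolute 50%-occupancy value is quoted, derive it as ED50 × 50 / (Occ_max − 50), and likewise for EC50, and report it as not reached when Occ_max is 50% or less.

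If the sponsor already intends Occ_max to be fixed at 100%, state that constraint in Section 6.1.3.1 instead; the present definitions are then correct. Fixing it only to rescue the definition would be a change of model, not of wording, and would need its own justification.

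The redefinition costs a wording change in two places, matching text in the SAP and at most one derived quantity per fitted model. Nothing changes in dosing, sampling or data collection.

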#### 6.1.4 Quetiapine pharmacokinetics

Pharmacokinetic variables for quetiapine and NDAQ will be derived from concentration-versus-time data obtained over a 24-hour pharmacokinetic sampling interval following SQL SR administration.

The following steady-state pharmacokinetic parameters will be determined:

$AUC_{ss}$	area under plasma concentration-time curve during any dosing interval at steady state (from 0 to 24 hours), calculated using the trapezoidal rule
$AUC(0-t)$	area under plasma concentration-time curve from time 0 until the last quantifiable plasma concentration up to 24 hours post-dose, calculated using the trapezoidal rule
$AUC_{PET}$	area under plasma concentration-time curve from start to stop of PET-assessment (planned at 5-7 hours post dose)
$C_{ss,max}$	maximum (peak) steady state drug concentration in plasma during dosing interval
$C_{ss,min}$	minimum (trough) steady state drug concentration in plasma during dosing interval
$C_{av,PET}$	average drug concentration in plasma during the PET-assessment, calculated as $AUC_{PET}/\text{duration of PET-assessment}$
$t_{max}$	time to reach peak or maximum concentration or maximum response following drug administration
$t_{1/2}$	the terminal elimination half-life (where calculable), where $t_{1/2} = \ln 2 / \lambda_z$ , where $\lambda_z$ is the terminal slope of the regression of $\ln$ concentration versus time curve

The following pharmacokinetic parameter will be determined for quetiapine alone:

CL/F apparent oral clearance, where  $CL/F = \text{Dose}/AUC_{ss}$

## **6.2 Safety evaluation**

### **6.2.1 Calculation or derivation of safety variables**

Safety and tolerability will be assessed in terms of AEs, vital signs, ECG, clinical chemistry, haematology, urinalysis, Bond-Lader VAS and pharmacokinetic variables.

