### **- Safety**

Adverse events, vital signs, ECG, clinical chemistry, haematology and urinalysis, Bond-Lader VAS.

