### 2.2 Secondary objective(s)

1. to characterize the pharmacokinetics of quetiapine and its metabolite NDAQ in the subjects undergoing PET analysis
2. to assess adverse events (AEs), vital signs and changes in laboratory parameters and Bond- Lader VAS ([Bond et al 1974](#))

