**Table 1 Study plan**

Visit	1	2	3	4	Residential period			5	
Visit Description	Enrolment	MRI Scana	PET Exam1a	Admission to CPU	SQL SR titration	SQL SR maintenance	PET Exam 2 after SQL SR dose	Discharge Follow-up	
Visit Window (Day)	Within -30 to -4 days	Within -29 to -1 days	Within -7 to -1 days	Day -1	Day 1-4b	Day 5-7b,c	Day 8	Day 9	5-9 days after last dose
Informed consent	X								
Demographic measurements	X								
Medical/surgical history	X								
Physical and neurological examination	X								X
Habits of nicotine, alcohol and caffeine	X								
Vital signs d	X				X e	X e	X	X	X
Electrocardiogram	X			X f		X g		X	
Inclusion/exclusion criteria	X								

Visit	1	2	3	4	Residential period			5
Visit Description	Enrolment	MRI Scan a	PET Exam1a	Admission to CPU	SQL SR titration	SQL SR maintenance	PET Exam 2 after SQL SR dose	Discharge Follow-up
Visit Window (Day)	Within -30 to -4 days	Within -29 to -1 days	Within -7 to -1 days	Day -1	Day 1-4b	Day 5-7 b,c	Day 8	Day 9
								5-9 days after last dose
Clinical chemistry/Haematology	X			X h				X
Urinalysis	X			X h				
Hepatitis B, C, and HIV	X							
Drugs of abuse screen	X							
Production of plaster helmet			X					
MRI		X						
PET after iv administration of (S,S)[18F]FMeNER-D2			X				X i	
Administration of SQL SR once daily in the morning					X	X	X	
Blood sampling for quetiapine PK							X j	

Visit	1	2	3	4	Residential period			5
Visit Description	Enrolment	MRI Scan a	PET Exam 1a	Admission to CPU	SQL SR titration	SQL SR maintenance	PET Exam 2 after SQL SR dose	Discharge Follow-up
Visit Window (Day)	Within -30 to -4 days	Within -29 to -1 days	Within -7 to -1 days	Day -1	Day 1-4b	Day 5-7 b,c	Day 8	Day 9
								5-9 days after last dose
Bond- Lader VAS k				X l	X	X	X	X
Adverse events m				X	X	X	X	X

- a) MRI and PET examination 1 cannot be done on the same day.
- b) In panel B and C the titration period may be removed (i.e. if dose is set to 50 mg) or changed to two days (i.e. if dose is set to 150 mg). The range of total time at CPU may thus be from 6 to 10 days for panel B and C.

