- c) In the unexpected event of technical failure (camera breakdown or the radioligand synthesis fails), the PET examination has to be moved to the nearest working day. Then it is done during the nearest days. In this case the SQL SR maintenance dosing period will be prolonged by 1-3 days (three days if it is moved from Friday to Monday). If this occurs the time the healthy volunteers are confined to the CPU will be prolonged.
- d) Vital signs includes pulse, systolic and diastolic blood pressure supine and again 2 min after standing.
- e) Vital signs will be assessed pre-dose and 6 hours post-dose during SQL treatment days, except for the PET 2 examination day, when vital signs will be assessed only pre-dose.
- f) ECG should be assessed prior to first titration dose, either day -1 or day 1.
- g) ECG should be assessed 6 hours post-dose the third day of steady state (maintenance dose).
- h) Blood sampling for a reduced Clinical chemistry/Haematology and Urinalysis should be repeated on the day of admission to the CPU if these samples were taken (at Enrolment visit) more than 1 week ago.
- i) Radioligand (S,S) [F]F MeNER-D2 to be injected 3.5 h (210 min) post-SRQ SR dose.  
PET measurements to start approximately 5 h post-SQL SR dose.
- j) Venous blood for PK analysis are to be taken 15 min pre-SQL SR dose, and 1, 2, 3, 4, 5, 6, 7, 8, 10, 12 and 24 h post-SQL SR dose.
- k) Bond-Lader VAS should be in the morning pre-dose.
- l) Training –Bond-Lader VAS
- m) Adverse Events (AEs) must be recorded from the admission to the CPU and until the follow up visit. Serious Adverse Events (SAEs) must be recorded from the time when the informed consent is obtained until the follow-up visit.

[figure not shown]

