### **4.3 Pharmacodynamic measurements (Not applicable)**

### **4.4 Safety measurements**

#### **4.4.1 Laboratory safety measurements**

Blood and urine samples for determination of laboratory variables will be taken at the times given in the Study Plan (Table 1) and the time schedule during confinement at CPU/PET centre (Table 2). The date and time of collection will be recorded on the appropriate CRF.

Samples will be collected in tubes according to standard routines. Blood volumes to be taken are described in Table 4.

The following laboratory variables will be measured:

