Adverse events m				X	X	X	X	X	X

- a) MRI and PET examination 1 cannot be done on the same day.
- b) In panel B and C the titration period may be removed (i.e. if dose is set to 50 mg ) or changed to two days (i.e. if dose is set to 150 mg). The range of total time at CPU may thus be from 6 to 10 days for panel B and C.
- c) In the unexpected event of technical failure (camera breakdown or the radioligand synthesis fails), the PET examination has to be moved to the nearest working day. Then it is done during the nearest days. In this case the SQL SR maintenance dosing period will be prolonged by 1-3 days (three days if it is moved from Friday to Monday). If this occurs the time the healthy volunteers are confined to the CPU will be prolonged.
- d) Vital signs include pulse, systolic and diastolic blood pressure supine and again 2 min after standing.
- e) Vital signs will be assessed pre-dose and 6 hours post-dose during SQL treatment days, except for the PET 2 examination day, when vital signs will be assessed only pre-dose.
- f) ECG should be assessed prior to first titration dose, either day -1 or day 1.
- g) ECG should be assessed 6 hours post-dose the third day of steady state (maintenance dose).
- h) Blood sampling for Clinical chemistry/Haematology and Urinalysis - As no fasting samples will be collected at the enrolment visit, fasting glucose and lipids should be performed on Day 1 of admission to the CPU. If the samples taken at the Enrolment visit are more than 1 week old, all samples have to be repeated. At Day -1 and Day 8 the healthy volunteers will be fasting from 22.00, water is allowed, sample collection should take place in the morning before administration of SQL dose.
- i) Radioligand (S,S) [F]F MeNER-D2 to be injected 3.5 h (210 min) post-SRQ SR dose. PET measurements to start approximately 5 h post-SQL SR dose.
- j) Venous blood for PK analysis are to be taken 15 min pre-SQL SR dose, and 1, 2, 3, 4, 5, 6, 7, 8, 10, 12 and 24 h post-SQL SR dose.
- k) Bond-Lader VAS should be in the morning pre-dose.
- l) Training –Bond-Lader VAS
- m) Adverse Events (AEs) must be recorded from the admission to the CPU and until the follow up visit. Serious Adverse Events (SAEs) must be recorded from the time when the informed consent is obtained until the follow-up visit.

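### Urinalysis is listed as a safety variable, but its row in the amended Table 1 has no end-of-treatment mark and does not agree with footnote h

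*Protocol*

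**What the plan says.** Two places in the protocol name urinalysis as safety data. The synopsis, under Safety, gives "Adverse events, vital signs, ECG, clinical chemistry, haematology and urinalysis, Bond-Lader VAS". Section 6.2.1 gives "Safety and tolerability will be assessed in terms of AEs, vital signs, ECG, clinical chemistry, haematology, urinalysis, Bond-Lader VAS and pharmacokinetic variables". Section 4.4.1 defines urinalysis as a protein and a glucose dipstick and leaves the timing of blood and urine samples to Tables 1 and 2. The second secondary objective in section 2.2 is "to assess adverse events (AEs), vital signs and changes in laboratory parameters and Bond- Lader VAS".

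With column spacing removed, the urinalysis row of Table 1 reads "Urinalysis X X h": one mark at enrolment and one that carries footnote h. In the amended Table 1 the second mark stands in the Day 1-4 column. The clinical chemistry/haematology row has the same two occasions and a third, also carrying footnote h, at discharge.

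The current footnote h, in the amended table, is headed for clinical chemistry/haematology and urinalysis together. It asks for fasting glucose and lipids on Day 1 and for all samples to be repeated if the enrolment samples are more than one week old. It has subjects fast from 22.00 at Day -1 and Day 8, and adds that "sample collection should take place in the morning before administration of SQL dose".

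**The concern.** A variable can speak to the safety and tolerability of a drug only if it is measured at least once after dosing begins. Vital signs, ECG, Bond-Lader VAS, adverse events and chemistry/haematology all have such an occasion in Table 1. Urinalysis appears to have none, although it stands in the same lists.

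Under section 6.3.3, safety variables are reported in subject listings and, if applicable, summary statistics. If the site follows the row as printed, the study report could hold only pre-treatment urinalysis under a safety heading. An inattentive reader might take that as showing no change when no change was measured. A statistical analysis plan cannot repair this, because the samples would not exist.

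**Working it through.** No figure in the plan needs to be reproduced. The check counts scheduled occasions and reads each one against its footnote.

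**Urinalysis, amended Table 1**
- Enrolment: one mark, before any dose.
- Day 1-4 column, footnote h: one mark. The footnote ties the admission sampling to Day 1 and to the time before the dose, so this is a baseline value. Urinalysis is not among the fasting tests always taken then, so the sample is due only if the enrolment sample is more than one week old.
- Later columns: no mark.
- Pre-dose occasions: 1 to 2. Occasions after the first dose: 2 marks - 2 pre-dose marks = 0.

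**Clinical chemistry/haematology, amended Table 1**
- Three marks, two of them before the first dose. Occasions after the first dose: 3 - 2 = 1.

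**Other places where a urine sample could be scheduled**
- Table 2 (the Day 8 schedule) has no urine collection, before or after the amendment.
- Section 4.1.2 gives the follow-up visit a physical examination and vital signs only.

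**Planned post-dose results over the study, with 6 to 9 subjects**
- Urinalysis: 0 x 6 = 0 to 0 x 9 = 0.
- Chemistry/haematology: 1 x 6 = 6 to 1 x 9 = 9.

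**Row against footnote.** The fast that begins at 22.00 on Day 8 fits a collection on the morning of Day 9, the discharge day, which is where the third chemistry/haematology mark stands. The heading of the footnote includes urinalysis in that sampling. The urinalysis row has no mark there. The two parts of the table therefore give different answers on whether urine is collected at the end of treatment.

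**Dependence on table layout.** Columns may have shifted when the table was read from PDF, but the count of marks (two against three) does not depend on alignment. The body of the protocol prints a different footnote h, under which samples "should be repeated on the day of admission to the CPU if these samples were taken (at Enrolment visit) more than 1 week ago". The amended table supersedes it, and the point does not rest on it. The row count was two against three there as well.

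**The case against.** The best counter-argument is that the current footnote h treats the three tests as one collection and names a late occasion. On that reading the end-of-treatment urine sample is intended, and only a mark is missing. This is plausible. It limits the point to an inconsistency within Table 1, but the inconsistency stays: a site that works from the row would take no urine at discharge.

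A reader might go further and infer that secondary objective 2 cannot be met. The documents do not support that. The objective speaks of "changes in laboratory parameters" without naming urinalysis, and chemistry and haematology have both baseline and post-dose samples. A reader might also infer that the sponsor deliberately excluded urine sampling after dosing. The footnote heading speaks against that.

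Three further objections have some force.
- The lists in the synopsis and section 6.2.1 name categories of safety data and do not promise a change from baseline for each. That is so, but pre-dose values alone still cannot assess the tolerability of the drug.
- Section 4.4.1 allows repeat sampling when a value is suspected to be clinically significant. Such a repeat is triggered by an abnormal result and gives no planned post-dose value for all subjects.
- Plasma glucose, creatinine and urea are in the chemistry panel, so related information is collected. This lowers the stakes but does not supply a urine result.

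Using urinalysis for eligibility only would be an ordinary choice. If that is the intention, the two safety lists describe it wrongly.

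**Conclusion.** The point holds as a minor inconsistency. The synopsis and section 6.2.1 count urinalysis as a safety variable, while the amended Table 1 schedules it only at enrolment and before the first dose. The row also disagrees with its own footnote h. Followed as marked, 0 of 6 to 9 subjects would have a planned post-dose urinalysis, so no change in it can be assessed. Chemistry and haematology are unaffected and can serve secondary objective 2.

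This rests on two assumptions: that the marks in the row, and not the footnote heading, decide what is collected, and that the third chemistry/haematology mark belongs to discharge, as the Day 8 fast suggests. If the footnote governs, the defect is one omitted mark.

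The primary occupancy objective is untouched. The variable is two dipstick items, reported descriptively, in healthy volunteers dosed for four to eight days.

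**What to change.** Reconcile the urinalysis row with footnote h. The preferred change is to add a urinalysis mark at discharge, using the existing protein and glucose dipstick at the collection where chemistry/haematology is already drawn. The cost is one dipstick per subject, 6 to 9 in all, at a visit that is already scheduled.

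If no end-of-treatment urine sample is wanted, remove urinalysis from the safety-variable lists in the synopsis and section 6.2.1, describe it as screening/baseline only, and limit its mention in footnote h to the pre-dose occasion. That costs a wording change, and the report then makes no statement on urinalysis under treatment.
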